11.3 Final Analysis Plan

Data quality. Before we carry out any statistical analyses, we will audit the data for quality and completeness. We will examine variable distributions for outliers and ensure that the data distributions meet the assumptions of the planned analysis. We will present the baseline characteristics as means and standard deviations for continuous variables and as counts and percentages for categorical variables. All inferential tests will be carried out at a two-tailed alpha level of .05.

Missing data. We will examine rates and patterns of missingness. If the missing at random (MAR) assumption is met, a common occurrence, we will perform multiple imputation (MI) analysis to impute missing outcome values when the rate of missingness is between 10% and 50%. Results will be reported for both the imputed data sets and a data set including only those who had complete data (“completers only”) for comparison purposes.

Primary Objectives. To quantify the incidence and prevalence of biologic complications and prosthetic complications among patients receiving dental implant therapy in a private practice setting.

For biologic complications, three binary outcomes will be examined: Peri-implant mucositis, Peri-implantitis and implant failure. For prosthetic complications, six binary outcomes will be examined including loosening of screws, screw fracture, structural fracture, resin or porcelain fractures, loss of retention, and abutment/ implant misfit. For the primary analysis, all outcomes will be defined at the person level and will be binary (Y/N) regardless of the number of complications experienced per participant. The 3-year cumulative incidence will be calculated as a ratio, where the numerator will be the total number of persons with one or more new (not existing at baseline) complications by the end of the follow-up period, and the denominator will be the total number of persons at risk for that complication at baseline. The prevalence will be calculated using the total number of persons with a complication (both new and existing) divided by the total number of persons at risk during each time interval (baseline, year 1, 2, and 3). In addition, the incidence and prevalence will be computed separately by age group, DM, smoking status, medication use, Osteoporosis, Radiation therapy, Periodontitis diagnosis, and Gingivitis diagnosis. We will calculate incidence and prevalence for all complications except implant failure (incidence only). If data permits, we'll also examine the number and rates of repeated prosthetic complications and the disease progression in biologic complications (mm bone loss over time) for exploratory analysis.

Secondary Objectives. To examine risk factors for biologic and prosthetic complications among patients receiving dental implant therapy in a private practice setting.

The unit of analysis for the secondary objectives are at the implant level for the biologic complications and the prosthesis level for the prosthetic complications. All the outcomes are binary outcomes (Y/N), and for primary analysis only the first occurrence will be considered. Multiple implants/ prostheses are clustered within the same patient, and multiple patients clustered within practitioners. To account for these correlations, General Estimating Equations (GEE) will be used to identify practitioner, patient and implant variables that are associated with the complications. A binomial model with a logit link function will be used for these binary outcomes. Separate analyses will be conducted for each complication. The variables in table 3 will be considered as potential risk factors.

Secondary analysis will evaluate the association between patient/implant/prosthetic risk factors and the rates of repeated prosthetic complications and the disease progression in biologic complications. For the rates of prosthetic complications, the outcome will be the number (count) of prosthetic complications during the 3-year follow-up period. The unit of analysis will be at the person level, and Poisson models will be used to identify practitioner, patient and prosthesis risk factors that are associated with a higher rate of prosthetic complications. For disease progression in biologic complications, the outcome will be mm bone loss (continuous) over time. Mixed effects model will be used to

account for the longitudinal nature of the data and to identify the practitioner, patient and implant risk factors that are associated with a higher amount of bone loss.

Table 3.

Practitioner level factors	
Number of implants restored per month	biologic and prosthetic complications
Years in practice	biologic and prosthetic complications
Post graduate education	biologic and prosthetic complications
Specialty training	biologic and prosthetic complications
Patient level risk factor	outcome
Age at baseline	biologic and prosthetic complications
Diabetes Mellitus	biologic complications
Smoking status	biologic complications
Medication use SSRI Bone sparing drugs Corticosteroid use	biologic complications
Osteoporosis	biologic complications
Radiation therapy	biologic complications
Periodontitis diagnosis	biologic complications
Gingivitis diagnosis	biologic complications
Parafunctional habits	prosthetic complications
Implant/ Prosthesis level risk factor	
Bone Grafting at time of implant placement	biologic complications
Immediate loading	biologic complications
Reason for tooth loss: Periodontitis	biologic complications
Reason for tooth loss: Endodontic failure	biologic complications
Reason for tooth loss: Caries	biologic complications
Reason for tooth loss: Trauma	biologic complications
Congenitally missing	biologic complications
Removable prosthesis	biologic complications
Poor prosthetic fit	biologic complications
Emergence angle	biologic complications
Cement remnants present	biologic complications
Open contacts present	biologic complications
Single tooth restoration	biologic and prosthetic complications
Multiple unit restoration splinted	biologic and prosthetic complications

Cemented restoration	biologic and prosthetic complications
Custom abutment	biologic and prosthetic complications
Stock abutment	biologic and prosthetic complications
Removable prosthesis full arch	prosthetic complications
Removable prosthesis: poor retention	prosthetic complications
Screw retained prosthesis	prosthetic complications
Opposing dentition: Natural	prosthetic complications
Opposing dentition: Complete denture	prosthetic complications
Opposing dentition: Partial denture	prosthetic complications
Occlusion: Mutually protected	prosthetic complications
Occlusion: Group function	prosthetic complications
Prosthesis material: Porcelain	prosthetic complications
Prosthesis material: Zirconia	prosthetic complications
Prosthesis material: Plastic	prosthetic complications
Prosthesis material: Zirconia with Porcelain veneer	prosthetic complications

Tertiary (exploratory) Objectives. To explore the OHRQoL (Oral Health-Related Quality of Life) following implant therapy, and to explore patient/implant/therapy level factors associated with patient satisfaction and OHRQoL.

The data from the OHRQoL will be used to quantify overall satisfaction with implant therapy and quality of life post-implant therapy, and will be presented at each time point to explore any potential time trend. In addition to baseline demographics and clinical factors, the type and location of prosthesis as well as the different types of complications will be included in correlation analysis with the OHRQoL survey data (Table 2). Because the OHRQoL score is a continuous variable, mixed effects model will be used to examine the association between these patient/implant/therapy factors and the OHRQoL score to account for the longitudinal nature of the data.

Table 4.

Patient level factors
Age at baseline
Diabetes Mellitus
Smoking status
Peri-implant mucositis
Peri-implantitis
Implant failures
Periodontitis diagnosis
Gingivitis diagnosis
Parafunctional habits

Implant/ Prosthesis level factors
Removable partial prosthesis
Poor prosthetic fit
Fixed prosthesis
Open contacts present
Single tooth restoration
Multiple unit restoration splinted
Cemented restoration
Screw retained prosthesis
Custom abutment
Stock abutment
Removable prosthesis full arch
Fixed full arch prosthesis
Prosthesis material: Porcelain
Prosthesis material: Zirconia
Prosthesis material: Plastic
Prosthesis material: Zirconia with Porcelain veneer

Practitioner level factors
Number of implants restored per month
Years in practice
Post graduate education
Specialty training

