3 OBJECTIVES AND OUTCOME MEASURES

3.1 Primary

Objective	Brief Description/Justification of Outcome Measure	Outcome Measured By	Time Frame

To quantify the incidence and prevalence of biologic complications amongst patients receiving dental implant therapy in a private practice setting.
	
Biologic complications will be defined as an implant that presented with measured bone loss on the radiographs and/or bleeding on probing, or failed implant. Biologic complications will be defined as a) Peri-implant mucositis: Bleeding on Probing (BoP) and/or purulent exudate without measured bone loss, or b) Peri-implantitis: measured bone loss on the radiographs, or c) Implant failure: an implant that has been lost or is planned to be removed
 
Incidence estimation will be based on a Poisson model for incidence per implant and year of follow-up.
	
a) The presence or absence of Bleeding on Probing (BoP) is measured by the practitioners at the annual evaluation visits and recorded in the annual follow-up surveys.
 
b) The radiographic bone changes are measured on the radiographs by calibrated examiners, utilizing the known geometry of the implant to convert to mm of bone change. Bone loss is defined as the negative change of the bone level measurements from the baseline radiographs taken at the time of prosthetic insertion.
 
c) Implant Failure: absence or planned removal of implant
	
Baseline data are collected at the time of prosthesis insertion and at each of the three annual follow-up visits.
 
The radiographs taken for clinical care purposes at prosthesis insertion and the 1, 2 and 3-year follow-up visits that are approved by the study team to be added to the radiograph repository will be utilized for radiographic assessments.

Objective	Brief Description/Justification of Outcome Measure	Outcome Measured By	Time Frame

To quantify the incidence and prevalence of prosthetic
	
Prosthetic complications will be defined as any complication that has compromised the esthetics
	
At baseline, practitioners will record surgical data (implant brand, size
	
Baseline surgical and specific prosthetics data

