- Practitioners will submit digital radiographs of each study implant, taken at baseline (after implant prosthetic placement) and at annual follow-up visits 1, 2, and 3 years following prosthetic placement. The radiograph should be void of any identifiers. Radiographs will be uploaded to the centralized study database provided by the NCC. The study team completes the final review to determine whether the radiograph is sufficient quality to be included in the radiograph repository. If the radiograph is insufficient quality, the study team will work with the Node Coordinator to provide feedback, if applicable, and determine whether a higher quality radiograph can be found. Radiographs in the radiograph repository will go through the adjudication process, where trained and calibrated evaluators assess the radiograph for quality and will determine peri-implant bone height measurements and prosthetic fit for each implant.
- Depending on the patient's enrollment date and whether future funding is obtained, a patient may not complete all study visits. If that occurs, the NCC, study team, practitioner, and/or Node Coordinator will reach out to the participants to inform them of the study status and future visits.
- If an implant has been removed since the last study visit, the practitioner will note this in the CRFs. The practitioner will complete the CRFs in relation to the situation prior to removal. No additional study visits will occur for the removed implant.
-

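### Three-year incidence counts patients lost without an event as complication-free wherever the imputation rule is not triggered, and it conflicts with the Poisson rate in Section 3.1

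*Protocol*

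**What the plan says.** Section 11.3 (Primary Objectives) defines the main estimate at person level: "The 3-year cumulative incidence will be calculated as a ratio". The numerator is persons with at least one new complication by the end of follow-up. For the denominator, "the denominator will be the total number of persons at risk for that complication at baseline". Neither part refers to time observed.

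Section 11.3 (Missing data) gives the only remedy. It is conditional in two ways: "If the missing at random (MAR) assumption is met, a common occurrence, we will perform multiple imputation (MI) analysis", and then only to "impute missing outcome values when the rate of missingness is between 10% and 50" per cent. Nothing is stated for missingness outside that range or for the case where the assumption is judged not met. A comparison analysis uses "a data set including only those who had complete data"; what counts as complete is not defined.

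Section 4 expects incomplete follow-up. Depending on enrolment date and funding, "a patient may not complete all study visits". It also ends observation of a failed implant once the removal has been recorded: "No additional study visits will occur for the removed implant". Section 5.5.2 stops study data for most withdrawals.

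Section 3.1 states a different method for the same two primary objectives: "Incidence estimation will be based on a Poisson model for incidence per implant and year of follow-up".

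**The concern.** A ratio over the full baseline risk set is a valid 3-year cumulative incidence only if everyone is followed for three years or has the event first. A patient who leaves event-free after one year stays in the denominator for all three years and can never enter the numerator. Unless that outcome is imputed, the estimate is too low.

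The gates on imputation sit badly. Above 50%, which a funding shortfall could produce, the crude ratio is furthest from the truth and no repair is planned. Below 10%, the bias can still match the precision the study is designed to deliver. Missing at random cannot be verified from the observed data, so it is a poor switch for the repair.

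The quantity affected is the primary result. Because Section 3.1 names another estimator, a reader also cannot tell which incidence the study will report.

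**Working it through.** **1. The plan's own precision.** Section 11.2 gives N = 16P(1−P)/W², so W = 4√(P(1−P)/N).
- P = 0.50, N = 1400: W = 4 × 0.5/√1400 = 0.0535 (Table 1: 0.053), half-width 2.7 points. N = 800 and 500 give 0.0707 and 0.0894 (Table 1: 0.071 and 0.090).
- P = 0.20, N = 1400: W = 4 × 0.4/√1400 = 0.0428 (Table 1: 0.043), half-width 2.1 points.

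Table 1 is reproduced.

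**2. Inputs that the protocol does not give (my assumptions).** Constant hazard, loss unrelated to outcome, and lost patients keeping only events seen up to their last visit. For loss levels I read two Table 1 columns as patients followed out of 1550: 1 − 1400/1550 = 9.7% and 1 − 500/1550 = 67.7%.

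**3. Formula.** With true 3-year incidence P, cumulative incidence is F₁ = 1 − (1−P)^(1/3) at year 1 and F₂ = 1 − (1−P)^(2/3) at year 2. If f₀, f₁ and f₂ are the shares never seen, last seen at year 1 and last seen at year 2, the unimputed ratio is

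R = f₁F₁ + f₂F₂ + (1 − f₀ − f₁ − f₂)P.

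- P = 0.50: F₁ = 0.2063, F₂ = 0.3700. With even loss, the average among those lost is (0 + 0.2063 + 0.3700)/3 = 0.1921.
- P = 0.20: F₁ = 0.0717, F₂ = 0.1382, average 0.0700.

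**4. Results where imputation may not be triggered.**

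| True P | Loss pattern | R | Bias (points) | Outcome unknown |
|---|---|---|---|---|
| 50% | 9.7%, even | 0.9032×0.5 + 0.0968×0.1921 = 47.0% | −3.0 | 0.0968×0.8079 = 7.8% |
| 50% | 5% after year 1, 5% after year 2 | 0.45 + 0.0103 + 0.0185 = 47.9% | −2.1 | 0.05×0.7937 + 0.05×0.6300 = 7.1% |
| 50% | 67.7%, even | 0.3226×0.5 + 0.6774×0.1921 = 29.1% | −20.9 | 0.6774×0.8079 = 54.7% |
| 20% | 9.7%, even | 0.9032×0.2 + 0.0968×0.0700 = 18.7% | −1.3 | 0.0968×0.9300 = 9.0% |

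The even-loss rows lie outside the 10–50% band whether missingness means incomplete follow-up or an unknown outcome. The second row is at 10% on the first count and 7.1% on the second, so whether imputation applies depends on a count that the protocol does not define. At 9.7% loss with P = 50%, R runs from 45.2% (all lost before year 1) to 48.7% (all lost after year 2).

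**5. The two incidence definitions.**

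| | Section 3.1 | Section 11.3 |
|---|---|---|
| Unit | implant (about 2000) | person (about 1550) |
| Quantity | rate per year of follow-up | proportion over 3 years |
| Unequal follow-up | enters through person-time | ignored |

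With 2000/1550 = 1.29 implants per patient, the units are not interchangeable. Hypotheses 1 and 2 in Section 11.1 use the cumulative form.

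**6. Completers-only and implant failure.** The answer depends on the undefined term. If complete means the yes/no outcome is known, no recorded failure is dropped. If it means all visits attended, a patient whose only implant is removed before year 3 is dropped. If the 450 extra implants sit in patients with 2 to 10 implants each, there are 1550 − 450 = 1100 to 1550 − 50 = 1500 single-implant patients, who hold 55% to 75% of implants. With failures spread evenly over three years, two thirds precede the year-3 interval, so 0.55×2/3 = 37% to 0.75×2/3 = 50% of failures are dropped.

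**The case against.** The strongest reply is that the plan does provide imputation, and that it works where it applies. A reader might infer that every primary incidence is biased downwards; the documents do not support that. If 5%, 10% and 15% are never seen, seen to year 1 and seen to year 2, the unimputed ratio at a true 50% is 42.6%; with 5%, 10% and 35% it is 40.0%. Both patterns fall inside the band: 30% and 50% have incomplete follow-up, and about 22% and 35% have unknown outcomes. Under missing at random, imputation would largely remove that bias. This stands.

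Three further readings are tempting and go too far.
- That the plan itself expects 9.7% loss. Section 11.2 never calls 1400 a retained number; it is one of three columns.
- That the completers-only set drops most implant failures by design. Section 11.3 leaves the term undefined, Section 4 records the removal and ends visits for the implant rather than the patient, and the set serves only for comparison.
- That imputation would create outcomes for implants already removed. A recorded failure is not a missing value, and nothing says that later visits would be imputed.

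It can also be said that estimator detail belongs in a statistical analysis plan, which is not at hand. That does not answer the point: the protocol itself fixes the ratio, its denominator and both gates, and Section 3.1 fixes a competing method.

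**Conclusion.** The point holds in limited form. Outside the 10–50% band, or where missing at random is judged not met, the stated ratio has no rule for incomplete follow-up and is biased downwards. Below 10% loss the bias cannot exceed 10% of the true value: under 5 points for a 50% outcome and under 2 points for a 20% outcome. For a 50% outcome it can therefore exceed the planned half-width, depending on when patients leave; for a 20% outcome it stays within it. Above 50% the error can be around 20 points. These sizes rest on a constant hazard, non-informative loss and assumed loss patterns, because the protocol gives no attrition rate.

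The conflict between Sections 3.1 and 11.3 needs no assumption: the unit and the estimand differ for the same primary objectives. The completers-only concern is an undefined term that needs one sentence, not a demonstrated loss of failures.

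**What to change.** 1. Choose one primary incidence definition and reconcile Section 3.1 with Section 11.3. The hypotheses in Section 11.1 fit a person-level 3-year cumulative incidence; an implant-year rate could be kept as a supplementary measure.
2. Either estimate it by a life table on the annual visits, with practitioner-clustered variance, treating implant removal as the event for failure and as a competing event for the other outcomes; or keep the ratio and remove both gates, so that missing outcomes are always imputed.
3. Define a completer as a patient with the event observed or followed to year 3, so that a patient whose only implant failed early stays in the comparison set.

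The cost is protocol wording and modest programming, with no new data. The estimate then relies on censoring being independent given covariates, which is no stronger than the missing-at-random assumption already planned. Neither route protects against informative loss.

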
complications amongst patients receiving dental implant therapy in a private practice setting.
	
and/or function of the implant restoration.
 
Incidence estimation will be based on a Poisson model for incidence per implant and year of follow-up.
	
and diameter, surgical therapy and site development, healing complications) and prosthetic data (type of restorations, abutment, restorative material, and occlusal scheme). At follow-up, practitioners will collect clinical data and record the presence or absence of the following complications on the prosthetics data collection survey: loose or lost screw, screw fracture, structural fracture, resin or porcelain fractures, loss of retention, abutment/implant misfit.
	
will be collected at the insertion of the prosthesis. The annual follow-up surveys at years 1-3 will record the presence or absence of prosthetic complications.

--	--	---	---

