4 STUDY DESIGN

- This is a prospective, observational 3-year cohort study of patients who undergo dental implant restoration by practitioners of the National Dental PBRN. Practitioners who restore dental implants will recruit and enroll their patients in this cohort study during the prosthetic phase of implant therapy.
- Approximately 200 practitioners from all 6 Network Nodes (approximately 35 practitioners per Node) will participate in the study, with each practitioner contributing approximately 10 patients and a maximum of approximately 50 implants.
- The patient population will comprise patients who plan to receive dental implant restorations provided by practitioners of the National Dental PBRN. Approximately 1550 patients will be enrolled until approximately 2000 implants are available for longitudinal observation. Implants will be clustered within patients and within approximately 200 dental practitioners across network practices. Each enrolled patient can contribute more than one implant if multiple implants will be restored at the baseline visit.
- Practitioner and practice characteristics from the National Dental PBRN Enrollment Questionnaire will be combined with data collected for this observational study.
- The prospective, observational study design will allow an opportunity to inform our knowledge of parameters for implant success and risk factors for biologic and prosthetic complications associated with implant therapy. The study will describe the implant restorative therapy provided by the practitioners, the incidence and prevalence of biologic and prosthetic complications, and will correlate patient-level factors, prosthetic- and implant-level characteristics with the risk for implant complications and the therapies provided for dental implant complications.

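### Repeated prosthetic complications are modelled as a person-level 3-year count with no stated exposure or practitioner clustering, at odds with the prosthesis-level and per-implant-year bases used elsewhere in the protocol

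*Protocol*

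**What the plan says.** Protocol section 11.3, under the secondary objectives, first sets the unit of analysis. For prosthetic outcomes it is "the prosthesis level for the prosthetic complications". It then describes the data structure: "Multiple implants/ prostheses are clustered within the same patient, and multiple patients clustered within practitioners". GEE is the stated remedy, in a paragraph about yes/no outcomes counted at first occurrence: "A binomial model with a logit link function will be used for these binary outcomes".

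The next paragraph turns to repeated prosthetic complications. There "the outcome will be the number (count) of prosthetic complications during the 3-year follow-up period". On unit and model it says: "The unit of analysis will be at the person level, and Poisson models will be used to identify practitioner, patient and prosthesis risk factors". The aim is to find those factors, in its words, "that are associated with a higher rate of prosthetic complications". It names no offset, denominator, cluster term or treatment of overdispersion for this model. It also gives no rule for assigning a prosthesis characteristic to a person.

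Three other places bear on the point:

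- Section 3.1, for the primary objectives: "Incidence estimation will be based on a Poisson model for incidence per implant and year of follow-up".
- Section 4: "Each enrolled patient can contribute more than one implant if multiple implants will be restored at the baseline visit". The same section says that some patients may not complete every visit and that a removed implant has no further study visits. Section 5.5 allows withdrawal.
- Section 11.3, under the primary objectives, calls the examination of numbers and rates of repeated prosthetic complications exploratory and dependent on the data permitting it.

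**The concern.** The stated target is a rate, but the stated outcome is a total per person. Followed as written, a patient with more prostheses or a longer observed period has a higher expected count at the same underlying risk. Any factor that travels with the number of prostheses or with follow-up time then picks up an association that is not about risk per prosthesis.

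The unit also fits the question poorly. Most candidate factors for prosthetic complications describe the prosthesis (retention, abutment, material, occlusion, opposing dentition), and a person with two different prostheses has no single value for them.

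Four candidate factors belong to the practitioner. These are the ones most exposed if correlation among a practitioner's patients is left out of the standard errors. The section recognises that correlation but links its remedy only to the binary models. At stake is which factors the registry reports as raising the rate of repeat complications.

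**Working it through.** **Plan's own figure.** The protocol gives no figure for the count model. The nearest that uses clustering is Table 2 (section 11.2), which concerns binary outcomes. It reproduces within 0.02 percentage points with 1400 × 1.4 = 1960 implants, equal groups, 80% power (power and total are assumptions), two-sided 0.05 and design effect 1 + (1.4 − 1) × ICC. At ICC 0.1 this gives 56.44% and 25.40%, against 56.43% and 25.40% printed. The cluster size of 1.4 is implants per patient, so the sizing does not cover practitioner clustering either.

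**Level of the candidate factors.** Counting the Table 3 rows marked for prosthetic complications: practitioner 4, patient 2, implant or prosthesis 17. Total 4 + 2 + 17 = 23.

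**Units per patient.** Section 4 gives about 1550 patients and 2000 implants, a mean of 2000/1550 = 1.29. There are 2000 − 1550 = 450 implants beyond the first, so at most 450 patients (450/1550 = 29%) have more than one, and at least 1100/1550 = 71% have exactly one. Since a splinted or full-arch restoration is one prosthesis on several implants, 29% is also an upper bound for patients with more than one prosthesis.

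**Observed time.** With the section 6 windows, a patient seen only at an early year-1 visit is observed to day 335, and one with a late year-3 visit to day 1245, a ratio of 1245/335 = 3.7. Among those completing year 3 the range is 1065 to 1245 days, a ratio of 1.17.

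**Bias without an exposure term.** Expected count = rate per prosthesis-year × prostheses × years. For a factor with no effect on the rate and equal follow-up, the fitted ratio is the ratio of mean prostheses. With assumed means of 1.6 and 1.2 it is 1.6/1.2 = 1.33.

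**Simulation (illustrative).** Assumptions:

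- 1550 patients, about eight per practitioner, and 300 runs per scenario.
- 0.022 to 0.10 complications per prosthesis-year, and 25% of patients with short follow-up.
- Practitioner SD of 0.3 to 0.8 and patient SD of 0.5 on the log scale.
- A null patient factor with 1.44 against 1.19 prostheses (ratio 1.21), and a null practitioner factor.

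| Null factor | Model | Rate ratio | False positives at 0.05 |
|---|---|---|---|
| Patient | No offset, model-based SE | 1.20 to 1.22 | 16% to 61% |
| Patient | Offset log(prostheses × years), clustered SE | 0.99 to 1.01 | 3% to 7% |
| Practitioner | Offset, model-based SE | – | 6% to 32% |
| Practitioner | Offset, clustered SE | – | 4% to 9% |

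Monte Carlo error on the false-positive rates is about 1 to 3 percentage points. When the patient factor was unrelated to the number of prostheses, the rate ratio without an offset was 1.00.

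**Practitioner clustering.** Patients per practitioner: 1550/200 = 7.75. Design effect DE = 1 + (7.75 − 1) × ICC. Standard-error shortfall = 1 − 1/√DE. The ICCs are assumed.

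- ICC 0.05: DE = 1.34, shortfall about 14%, true two-sided level about 0.09.
- ICC 0.10: DE = 1.68, shortfall about 23%, true level about 0.13.

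These hold for a factor constant within practitioner. For factors that vary within practitioner the inflation is generally smaller.

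**The case against.** The strongest reply is that most of this is silence. The protocol speaks of a rate, already has a per-implant-year Poisson basis in section 3.1, recognises both levels of clustering, and promises to check model assumptions. An offset, robust standard errors or a negative binomial fallback could sit in an analysis plan not shown. That is fair as far as it goes: these features are unstated, not excluded. A reader might infer that the protocol commits to a model without them, and the text does not go that far. It does, however, affirmatively choose the person as unit and a raw count as outcome, against its own earlier sentence and section 3.1. That conflict does not depend on what an analysis plan adds.

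Second, the missing-data paragraph provides for multiple imputation of missing outcomes and a completers-only analysis, and completers differ little in observed time. This weakens the follow-up part of the concern. A reader might suppose that shorter follow-up alone could produce a ratio of two thirds, but that needs one whole comparison group followed for two years and the other for three without imputation, which nothing in the protocol suggests. Imputation does nothing about differing numbers of prostheses.

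Third, a reader might infer that prosthesis factors cannot be assigned at all, or that splinted and full-arch work becomes a risk factor automatically. Neither is supported. At least 71% of patients have one implant and so an unambiguous value, and a full-arch restoration is a single prosthesis, so it adds no prosthesis exposure.

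Fourth, a person-level burden of complications is a legitimate target, summing to the person already absorbs within-patient correlation, and a separate prosthesis-level GEE covers first occurrences. All of this stands, and it limits the consequence.

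**Conclusion.** The concern holds in a limited form. As written, the repeat-complication model uses a unit and an outcome that conflict with the prosthesis-level unit in the same section and with the per-implant-year basis in section 3.1, and it suits poorly the 17 of 23 candidate factors that are not person-level.

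The bias is confined to factors associated with number of prostheses or observed time. Its size depends on how strong that association is, which the protocol does not give; 1.33 rests on the assumed means. The undefined-value problem affects only patients with prostheses of differing type, at most 29%. The standard-error shortfall of about 14% to 23% applies to practitioner-level factors and rests on assumed ICCs of 0.05 to 0.10. Overdispersion from repeated failures would add to it.

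It would be wrong to conclude that the registry's main results are at risk. The primary incidence and the binary GEE risk-factor analyses are untouched, and this model is secondary to them. The change is still worth making because it is cheap and the better basis is already in the protocol.

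**What to change.** In section 11.3, rewrite the paragraph on repeated prosthetic complications so that:

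- the outcome is the count per prosthesis, with log(years observed for that prosthesis) as offset;
- the model is Poisson GEE with robust standard errors, or negative binomial, clustered on practitioner with patients nested within;
- prosthesis factors enter at prosthesis level, with patient and practitioner factors carried down to each prosthesis.

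If a person-level burden analysis is also wanted, label it as such. Give it a log(prosthesis-years) offset and practitioner-robust standard errors, and state how prosthesis factors are coded for patients with prostheses of differing type.

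The cost is wording and modest programming. The count of prostheses, visit dates and practitioner identifiers are already part of the planned data, so nothing new needs to be collected.
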